**NCT#03849300**

## **Full study protocol (Control vs. Aquatic walking exercise group 1)**

### **Participants**

Participants were recruited with flyers and clinic referrals in a metropolitan city in South Korea at multiple community health centers where the members were primarily female. Study allocation was determined randomly with a computerized random number generator (**Figure 1**). All participants were female and classified as Fontaine stage I or II PAD with an ABI of 0.7 – 0.9. All participants were sedentary, defined as participating in under 1 hour of regular exercise participation per week within the previous year. Exclusion criteria included current smoker (smoking within  $\leq 6$  months), psychiatric conditions, as well as pulmonary, renal, and thyroid diseases. These exclusion criteria for these diseases were included to avoid any secondary disease effects on the target population used in the present study. All procedures were conducted in accordance with the protocols approved by the Institutional Review Board designated by Ministry of Health and Welfare (PNU IRB-2016\_92\_HR) and carried out in accordance with the Declaration of Helsinki, and all subjects provided written, informed consent prior to experimental measures. All protocols and lab procedures took place at the community centers. This study was registered with clinicaltrials.gov (NCT03849300).

### **Study design**

This study used a 2-armed parallel experimental design. Arterial stiffness, resting HR, BP, ABI,  $VO_2$ max, 6MWD, physical function scores, hand grip strength, leg strength, anthropometrics, RMR, and flexibility were assessed at baseline and after the 12 weeks. All measurements were performed at the same time of day (8:00 AM,  $\pm 1$  h) after a 12-hour fast. The  $VO_2$ max test and 6-minute walk test were separated by a period of  $\sim 24$  hours to prevent confounding effects of fatigue. Following baseline measurements, participants were randomly allocated to either the aquatic

walking training group (AQ,  $n = 35$ ) or the control group (CON,  $n = 37$ ). The AQ group participated in a supervised aquatic walking training program for 12 weeks that included a warm-up, main exercise session, and a cool-down. The CON group did not participate in any exercise program or perform any additional exercise. The CON group participants were present and supervised in the laboratory at the same frequency and time of day as the AQ group (10:00AM,  $\pm 1$ h) and performed sedentary activities such as reading books, listening to music, or learning new computer skills, which are among some of the activities these participants normally perform when attending the community center daily. The AQ and CON groups were advised to refrain from changing any dietary habits throughout the study period, and diet logs were given to researchers weekly to monitor caloric intake to ensure there were no changes in diet throughout the intervention. If researchers noticed differences in caloric intake, they advised participants to maintain their normal diet. Lunch and dinner were provided to participants at the community centers. All participants were supervised by qualified trainers and measurements were taken by experienced researchers, and researchers who performed the laboratory measurements were blinded to the randomization of subjects.

### **Exercise program**

Participants in the AQ group participated in an aquatic walking exercise training program for 12 weeks, 4 days per week, for 60 minutes per day (**Table 1**), and this was adapted from previous literature for older individuals and patients with PAD (3, 47). Sessions were conducted in waist-to-chest-deep water (28-30°C) in a group setting (3). Participants were allowed to use flotation devices as needed for safety purposes. Participant heart rate (HR) was monitored using a wearable Polar HR monitor (Electro, Oy, Kempele, Finland) during all exercise sessions to maintain the appropriate training intensity. The aquatic walking exercise training program

intensity was established using heart rate reserve (HRR) and Borg's revised rating of perceived exertion scale (RPE, 0 to 10 scale). HRR was calculated as  $(\text{HRR} = [\% \text{ intensity desired} * (\text{HR}_{\text{max}} - \text{HR}_{\text{rest}})] + \text{HR}_{\text{rest}})$ . The intensity of the program increased every 4 weeks: weeks 1-4 were at 50-60% HRR and 6-8 RPE, weeks 5-8 were at 60-70% HRR and 6-8 RPE, and weeks 9-12 were at 70-85% HRR and 6-8 RPE. Each training session was supervised, and each trainer was assigned to work with 10 participants during the sessions. HR monitors and RPE were checked every 5 minutes during the sessions. If the HR or RPE were too low or too high according to the intensity level, the participants were encouraged to either increase or decrease their effort during the exercise training session.

The program was divided into 3 sections including a warm-up (10 min), main exercise component (40 min), and a cool-down (10 min) (**Table 1**). Both the warm-up and cool-down included underwater stretching that emphasized lower limb muscles (quadriceps, hamstrings, hip abductors/adductors, and hip flexors) and low-intensity gait training (forward, backward, and lateral movement) (3). The main exercises were performed for a total of 40 minutes. The first 10 minutes of main exercises included simple movement patterns such as hip flexion-extension, hip abduction-adduction, and knee flexion-extension (3). The next 30 minutes of the main exercise session consisted of water walking exercises (forward, backward, lateral) (3).

### **Arterial stiffness, HR, BP, and ABI**

Participants rested in a supine position for 5 minutes. Femoral-to-ankle pulse wave velocity (legPWV), a measurement of peripheral arterial stiffness, was measured using applanation tonometry (TU-100 and VP-2000, OMRON Healthcare, Kyoto, Japan). A pulse wave sensor was placed on the femoral artery, while the cuffs with pulse wave sensors on the ankles and EKG electrodes remained in place from the ABI measurement. BP, EKG, and pulse waveforms were

simultaneously recorded for 10-30 seconds. Data analysis was performed according to the Clinical Application of Arterial Stiffness, Task Force III (69).

Participants rested in a seated position for 5 minutes. Resting HR, systolic BP, and diastolic BP were measured in duplicate using radial artery palpation and an automated sphygmomanometer (BP-200, OMRON, Kyoto, Japan), respectively, before and after 12 weeks. The average of the two measurements was recorded as the resting values. If the measurements differed by  $>5$  mmHg, an additional measurement was taken and the two closest readings (differed by  $\leq 2$  mmHg) were averaged (50). The interclass correlation coefficient in our laboratory for systolic and diastolic BP calculated on two measurements is  $\approx 0.97$ .

Participants rested in a supine position for 5 minutes. ABI was measured using the VP-2000 (OMRON, Kyoto, Japan). Electrocardiogram (EKG) electrodes were placed on the forearms. BP cuffs with pulse wave sensors were wrapped around both arms (brachial artery) and ankles (posterior tibial artery). Measurements were recorded for 10-30 seconds.

### **Cardiorespiratory capacity and 6-minute walking distance**

The Cornell modified Bruce treadmill test was used to determine the maximal volume of  $O_2$  consumption ( $VO_{2max}$ ) (32). This Bruce protocol modification has been proven to be valid and reproducible (48) and has been used in disease populations (76). The modified Bruce consists of 11, 2-minute stages that progress from 1.7 mph and 0% grade to 5 mph and 18% grade (48). The treadmill test was ended when the participants reached volitional fatigue. Expired gases were measured with a metabolic cart (OxyCon Pro, Viasys Healthcare, Conshohocken, PA).

The 6-minute walk test was used to determine maximal walking distance, or exercise tolerance. Participants were asked to walk as many laps as possible around a 100-meter track for 6 minutes.

## **Physical function**

Physical function was assessed collectively using physical function questionnaires from the Medical Outcomes Study Short-Form 36 General Health Survey (MOS SF-36) (73). Other parameters (i.e. not physical function domain) were not assessed using the MOS-SF 36. Physical function questionnaires of the MOS SF-36 are valid and reliable surveys that are often used for assessing physical function in patients with PAD (22, 24, 66, 73).

## **Muscular strength**

Upper body muscular strength was determined using maximal isometric handgrip strength with a standard handgrip dynamometer (JAMAR, Bolingbrook, IL). Measurements of the dominant hand were taken 3 times, and the best of the 3 trials was recorded as the measurement.

Lower body muscular strength was assessed using one-repetition maximum (1RM) on a leg extension machine (Cybex 6000; Lumex, Albertson, NY). The 1RM was measured with the dominant leg, and the 1RM was achieved within 5 or fewer attempts. The highest weight lifted using the proper form was recorded as the 1RM.

## **Anthropometrics**

Anthropometric measurements, including height, total body mass, body mass index (BMI), and body composition were measured before and after 12 weeks. Height was measured using a standard stadiometer to the nearest 0.1 cm. Body composition was estimated using bioelectrical impedance analysis (BIA) (InBody 230, Biospace, Seoul, Korea), which simultaneously recorded total body mass (nearest 0.1 kg), and body fat (nearest 0.1%) (60). BMI was calculated as body mass divided by the height squared ( $\text{kg}/\text{m}^2$ ).

## **Resting metabolic rate**

Resting metabolic rate was estimated using a metabolic cart (OxyCon Pro, Viasys Healthcare, Conshohocken, PA). Subjects remained in the supine position and were instructed to breathe normally and to not fall asleep during the measurement, and the measurements were performed for 30 minutes.

### **Flexibility**

Flexibility was measured using the YMCA sit-and-reach test. Each participant was given 3 attempts to reach as far as possible with proper form, and the best of the 3 trials was recorded as the score.

### **Statistical analysis plan**

The Shapiro-Wilk test was used to determine data normality. Independent *t* tests were used to determine any baseline differences between the AQ and CON groups. A two-way analysis of variance (ANOVA) with repeated measures [group (AQ and CON) x time (pre- and post-12 weeks)] was used to determine the difference of changes between pre- and post-aquatic walking training program within and between groups on the dependent variables. When a significant interaction was noted, paired *t* tests were used for post-hoc comparisons. All analyses were performed using SPSS 24 (SPSS Inc. Chicago, IL, USA). Data are presented as Mean  $\pm$  SD. Statistical significance was set to  $p < 0.05$ . Additionally, correlations between variables were assessed with Pearson product-moment correlations. A power analysis calculation was used to determine a minimum sample size of 64 (32 each group) would allow for the observation of a difference of 3-5% between groups (AQ vs. CON) for PWV with a power of 90% (4, 47).

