### **Study design**

A 2-armed parallel experimental design was used (**Figure 2**). Anthropometrics, vascular function, resting metabolic rate, walking capacity, COT, and muscular strength were assessed at baseline and after the 12 weeks. All lab assessments were performed at the same time of day (8:00 AM,  $\pm 1$  h) following an overnight fast. All participants were asked to abstain from medications for at least 24 hours prior to the baseline and post-exercise therapy measurements but continued taking medications throughout the exercise therapy protocols according to their physician

instructions. After baseline measurements, participants were allocated randomly to the HWET group (n = 28) or the LBET group (n = 25). The HWET group participated in a supervised heated-water exercise therapy program for 12 weeks. The LBET group participated in supervised treadmill therapy program for the same period of time. Both exercise groups were asked to refrain from altering dietary habits throughout the study period, and researchers obtained weekly diet logs from each participant to audit caloric intake. The exercise therapy sessions and experimental measures took place at the community centers. All participants were supervised by qualified trainers during exercise therapy sessions, and measurements were taken by experienced researchers who were blinded to participant randomization.

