### **Statistical analysis plan**

The Shapiro-Wilk test was used to assess normality of the data. Independent *t* tests were used to determine any baseline differences between the LBET and HWET groups. A two-way repeated measure analysis of variance (ANOVA) [group (LBET and HWET) x time (pre- and post-12 weeks)] was used to assess changes between pre- and post- LBET vs. HWET within and between groups on the dependent variables. When a significant interaction was found, paired *t* tests were used for post-hoc comparisons. All analyses were performed using SPSS 24 (SPSS Inc. Chicago, IL, USA). Statistical significance was set to  $p < 0.05$ . Data are presented as Mean  $\pm$  SD. A power analysis calculation was used to determine the minimum sample size of 50 (25 in each group) would allow for the observation of a change of 3-5% between groups (LBET vs. HWET) for legPWV with a power of 90% (4, 54).

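### An improvement at almost no cost, not an error: report the between-arm difference in change with its 95% CI, and add a baseline-adjusted ANCOVA

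*Combined protocol and SAP*

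**What the plan says.** The document holds two randomised comparisons, each with its own section headed Statistical analysis plan. Sub-study 1 compares aquatic walking (AQ, 35) with control (CON, 37). Sub-study 2 compares heated-water exercise (HWET, 28) with land-based exercise (LBET, 25).

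- Sub-study 1: "A two-way analysis of variance (ANOVA) with repeated measures [group (AQ and CON) x time (pre- and post-12 weeks)] was used". The aim is to compare changes "within and between groups on the dependent variables".
- Sub-study 2: "A two-way repeated measure analysis of variance (ANOVA) [group (LBET and HWET) x time (pre- and post-12 weeks)] was used".
- Follow-up in both is by paired t tests and depends on the interaction. Sub-study 2 has "When a significant interaction was found, paired" t tests, and sub-study 1 likewise says that paired t "tests were used for post-hoc comparisons".
- Results are to be shown as mean ± SD, with significance at p < 0.05.
- Baseline values are compared between arms by independent t tests and enter the ANOVA as one level of time. They are not a covariate.
- The Study design sections place baseline before allocation: "Following baseline measurements, participants were randomly allocated to either the aquatic" or control group in sub-study 1, and "After baseline measurements, participants were allocated randomly to the HWET group" or the land-based group in sub-study 2.

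Neither plan names a between-arm effect estimate, a confidence interval or a baseline covariate. No SD, pre-post correlation or slope appears anywhere in the document.

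**The concern.** The group-by-time test is sound in a randomised pre-post design. The question is what the plan leaves unused.

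**Estimate and interval.** The only follow-up is within each arm, and a paired t test within an arm does not estimate the difference between arms. If the interaction is not significant, there is no follow-up at all, and the reader is left with a p value and mean ± SD. That does not show how large an arm difference the data still allow. This matters most in sub-study 2, where both arms exercise and a non-significant result could be read as equivalence.

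**Precision.** A change score assumes that week 12 moves one for one with baseline. Because baseline was measured before randomisation, that slope can be estimated instead, which may narrow the interval with no new data.

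**Working it through.** **1. The planned test is a change-score comparison.** With two time points, the interaction F equals the squared two-sample t on change scores. On simulated data with arms of 35 and 37, both came to 7.938. The planned analysis therefore already contains the difference in mean change and its CI.

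**2. Mean ± SD at each visit does not give the interval.** Var(change) = s0² + s1² − 2·ρ·s0·s1, where s0 and s1 are the baseline and week-12 SDs and ρ is the pre-post correlation. The plan does not promise to report ρ. The Pearson correlations in sub-study 1 are between variables.

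**3. Width of the missing interval.** Arm sizes are from the Study design sections. All allocated participants are assumed to have both values, as completeness is not stated.

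Half-width = t(0.975, N−2) × √(1/n1 + 1/n2) × SD of change

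- 35 vs 37: 1.994 × 0.2358 = 0.470 SD of change
- 28 vs 25: 2.008 × 0.2752 = 0.552 SD of change

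An observed difference of zero would still allow about half an SD of change in either direction.

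**4. ANCOVA against the change score.** Let k = s1/s0. The slope of week 12 on baseline is b = ρk. For a normally distributed baseline and a common slope:

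Variance ratio = k²(1 − ρ²) / (1 + k² − 2ρk) × (1 + 1/(N−4))

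The last factor is the expected cost of estimating the slope. Before that cost, the change-score variance exceeds the ANCOVA variance by s0²(1 − b)², which is zero only at b = 1, that is, at ρ = s0/s1. The condition for no gain is a slope near 1, which is the same as a correlation near 1 only when the two SDs are equal.

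Worked example, N = 72, k = 1, ρ = 0.5: 0.75/1.00 × (1 + 1/68) = 0.761.

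Variance ratios at N = 72 (all ρ and k are assumed):

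| k | ρ = 0.5 | 0.7 | 0.8 | 0.9 |
|---|---|---|---|---|
| 0.8 | 0.580 | 0.637 | 0.649 | 0.617 |
| 1.0 | 0.761 | 0.862 | 0.913 | 0.964 |
| 1.1 | 0.830 | 0.935 | 0.982 | 1.014 |
| 1.25 | 0.906 | 0.995 | 1.015 | 0.964 |

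At N = 53, k = 1 gives 0.765, 0.867, 0.918, 0.969 and k = 1.25 gives 0.911, 1.001, 1.020, 0.969.

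As CI width at N = 72, t quantiles included:

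- k = 1: 12.7%, 7.1%, 4.4% and 1.8% narrower.
- k = 1.25: 4.8% narrower, 0.2% narrower, 0.8% wider, 1.8% narrower.

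The worst expected loss of variance is 1/(N−4): 1/68 = 1.5% at N = 72 and 1/49 = 2.0% at N = 53. Simulation with 40,000 trials per setting for k = 0.8, 1 and 1.25 agreed within about 0.01, with type I error of 4.8% to 5.2% for both methods.

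**5. Where a larger week-12 SD is plausible.** In sub-study 1, "All participants were female and classified as Fontaine stage I or II PAD with an ABI of 0.7" to 0.9; in sub-study 2 the range is 0.6 to 0.8. If the eligibility reading is also the baseline reading, a range of 0.2 caps the baseline SD at 0.2/2 = 0.10. Evenly spread values would give 0.2/√12 = 0.058. Week-12 values have no such limit. A week-12 SD of 1.25 × 0.0577 = 0.072 would be the k = 1.25 row. This is an illustration only.

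**The case against.** **ANCOVA here is a preference.** The planned test is valid, and the ratios run from 0.58 to 1.02 on assumed inputs. Nothing in the document supports the k = 0.8 row, which shows the largest gains. With equal SDs and ρ of 0.8 to 0.9, the interval narrows by only 2% to 4%. All of this is right, and it is why the point is an improvement of unknown size. What remains is the asymmetry: the expected loss is at most about 2% of variance, while the possible gain is much larger.

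**It may be too late.** The plans are in the past tense and give realised arm sizes. A supplementary ANCOVA would not sharpen the planned test, and it adds a second estimate for each of about a dozen outcomes. This stands, so the planned test should then keep its place.

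**The interval is narrow by the plan's own target.** Assuming two-sided 0.05, 90% power implies a standardised difference of (1.960 + 1.282) × √(2/32) = 0.81 in sub-study 1 and (1.960 + 1.282) × √(2/25) = 0.92 in sub-study 2 (0.82 and 0.94 with the t distribution). If the planning SD is the SD of change and holds, half-widths of 0.47 and 0.55 lie below these, and an observed zero for legPWV would exclude the planned difference. That is a fair limit on the worry about legPWV, but a reader can see it only if the interval is reported. It gives no reassurance for outcomes on which the study was not powered.

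**The interval can be recovered.** Arm means give the difference in change, and an exact p value gives its standard error. The plan does not promise exact p values, and rounding defeats the calculation when the difference is near zero.

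**Conclusion.** The point holds as an improvement to a valid analysis in both sub-studies.

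- **Estimate and interval:** the gap is one of reporting. Its size is a 95% half-width of 0.47 (sub-study 1) or 0.55 (sub-study 2) SD of change, assuming complete data. This cannot be put in PWV units because no SD is given.
- **ANCOVA:** it may add precision unless the slope of week 12 on baseline is near 1. The amount cannot be known from the document. Over the assumed grid the variance ratio runs from 0.58 to 1.02, given a common slope, a normal baseline and near 1:1 allocation.

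Confidence is high in the algebra and in the absence of these items from the text, but not in any particular gain.

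**What to change.** 1. In each sub-study, report the between-arm difference in mean change with its 95% CI for every continuous outcome, legPWV first, whether or not the interaction is significant. The cost is one extra column per outcome table, from the analysis already planned.
2. Fit the week-12 value on arm plus the baseline value of the same outcome, and report the adjusted difference with its 95% CI. The cost is one residual degree of freedom per model, with the same data and software.
   - If the data are not yet analysed, make this the efficacy analysis and show within-arm changes descriptively.
   - If they are analysed, as the document suggests, keep the interaction test as the planned analysis, add the interval in item 1, and give the ANCOVA in one table labelled supplementary.

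COT in sub-study 2 is outside this point.

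### The first study's Pearson correlations have no arm term: if 12-week or change values are pooled over arms, a shared training effect alone can make two outcomes correlate

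*Combined protocol and SAP*

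**What the plan says.** The combined document holds two study protocols. This point concerns the first, control (CON) against aquatic walking (AQ). The second study's analysis plan contains no correlation analysis.

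In the first study's Statistical analysis plan, after the t tests and the group-by-time ANOVA, a single sentence states that "correlations between variables were assessed with Pearson product-moment correlations". It does not say:

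- which variables are correlated;
- whether baseline, 12-week or change values are used;
- whether the arms are combined or analysed separately;
- whether arm is adjusted for;
- how many pairs are tested.

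The only threshold in the section is 0.05. The baseline t tests and the ANOVA in the same section both name AQ and CON; the correlation sentence does not.

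The Study design section gives 35 participants in AQ and 37 in CON, and says that CON did no exercise programme. It lists 12 outcome headings, ending with "physical function scores, hand grip strength, leg strength, anthropometrics, RMR, and flexibility were assessed at baseline and after the 12 weeks". The power statement aims at "observation of a difference of 3-5% between groups (AQ vs. CON) for PWV" with 32 per arm and 90% power, and gives no standard deviation.

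**The concern.** A Pearson correlation computed over both arms mixes two things: how outcomes go together among people in the same arm, and how far apart the arm means lie. The trial compares training with no training, so arm differences in trained outcomes are what it hopes to find. When two outcomes both shift with training, the arm means alone line them up. If stiffness falls and walking distance rises in AQ, the two correlate negatively in the combined sample, even if the participants whose stiffness fell most were not those who walked further.

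Such a correlation is readily read as a link between the two changes within individuals. Computed over both arms without adjustment, it may say no more than that the programme moved both outcomes, and it grows with the size of the training effect.

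**Working it through.** **Inputs from the documents.** 35 AQ and 37 CON (Study design); planned 32 per arm, 90% power, PWV difference of 3-5%, threshold 0.05 (Statistical analysis plan).

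**Assumptions.** Two-sided tests, normal data, equal within-arm SDs, zero within-arm correlation, and the same standardised arm effect d on both outcomes. The documents give no SDs, so d is shown as a range.

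**Step 1: the plan's own figure.** The sample size of 64 cannot be reproduced without an SD. It can be inverted for the effect it implies:

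d = (z0.975 + z0.90) × √(2/32) = (1.960 + 1.282) × 0.25 = 0.81.

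A t-based calculation gives 0.82, and a one-sided test would give 0.73. With d = 0.81, a 3% difference implies an SD of 3/0.81 = 3.7%, and a 5% difference an SD of 5/0.81 = 6.2%. This anchors d for PWV only.

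**Step 2: correlation produced by arm alone.** With p = 35/72, p(1 − p) = (35 × 37)/72² = 0.2498. If the within-arm correlation is zero, the pooled correlation is

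r = p(1 − p)d₁d₂ / √{[1 + p(1 − p)d₁²][1 + p(1 − p)d₂²]},

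which for d₁ = d₂ = d is 0.2498d² / (1 + 0.2498d²). At d = 0.81 this is 0.1639/1.1639 = 0.14. Effects in opposite directions give the same size with a negative sign.

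**Step 3: how often that is significant.** With n = 72 the critical |r| is 0.232. Rejection rates come from 40,000 simulated trials of 35 vs. 37 at each effect size. A false positive here means a significant r when the outcomes are unrelated within arms.

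| Arm effect on each outcome (SD) | Pooled r | Pooled Pearson, significant | Arm partialled out, significant |
|---|---|---|---|
| 0 and 0 (baseline values) | 0.00 | 4.8% | 4.9% |
| 0.81 and 0 | 0.00 | 5.1% | 5.2% |
| 0.3 and 0.3 | 0.02 | 5.4% | 4.9% |
| 0.5 and 0.5 | 0.06 | 7.9% | 4.9% |
| 0.81 and 0.81 | 0.14 | 21.8% | 5.0% |
| 1.0 and 1.0 | 0.20 | 40.5% | 4.9% |
| 1.5 and 1.5 | 0.36 | 91.0% | 4.9% |

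A Pearson correlation within AQ alone was significant in 4.8% to 5.1% of trials across these scenarios.

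**Step 4: number of pairs.** The 12 outcome headings make 12 × 11/2 = 66 pairs. If all were tested and all were null, 66 × 0.05 = 3.3 would be significant by chance. The plan neither states nor rules out testing them all.

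**The case against.** The strongest reply is that the plan does not describe the flawed analysis. It mentions correlations between variables and no more. Correlations at baseline, within AQ, or within each arm fit the sentence as well as pooled ones do, and none of these carries the bias. The problem needs two unstated choices: combining the arms, and using 12-week or change values. The correlations are also an addition to the ANOVA, which does include arm, and no between-arm conclusion in the plan rests on them. All of this stands, and it makes the point conditional and minor.

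A reader might go further and infer that every outcome is correlated with every other, that pre and post values are stacked so that each person counts twice, or that any two outcomes will show a spurious link. The documents support none of these. They do not name the variables or mention stacking. Even under pooling, the inflation is small at 0.5 SD or less and absent when only one outcome responds. At 0.81 SD on both outcomes, about 78% of such pairs would still not be significant. Nor do the documents say that the correlations will support statements about mechanism; that is only a common use.

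The reply does not remove the core. The stated method has no arm term, and the sentence allows a biased analysis and a sound one alike, with the choice open after the data are seen.

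**Conclusion.** The concern holds in conditional form and is low in severity. The plan states a plain Pearson correlation and leaves the time point and the handling of arms open. If 12-week or change values are correlated over both arms, shared training effects can raise the false-positive rate from 5% to about 8%, 22% or 40% at 0.5, 0.81 or 1.0 SD on both outcomes.

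The 0.81 comes from the plan's own sample size, but for PWV only. Applying it to a second outcome is an assumption, as are the other effect sizes, equal within-arm SDs and zero within-arm correlation. The SD unit behind 0.81 (12-week value or change) is not stated either. Baseline correlations, within-arm correlations and the group-by-time ANOVA are not affected.

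**What to change.** Replace the correlation sentence with:

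> Correlations are computed on individual changes (post minus pre), one value per participant, as partial correlations controlling for arm (or separately within arm). All are exploratory, and the number of pairs tested is reported with false discovery rate control.

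The choice between the two forms should be stated. A partial correlation uses all 72 participants but assumes the same relation in both arms. Within-arm correlations drop that assumption at the price of smaller samples. The plan already reports realised group sizes, so calling any pairs prespecified now would not be credible; hence the exploratory label for all of them.

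The cost is small: one sentence, a standard procedure, no new data, and a re-run on existing data if the analysis is complete. The downside is that fewer correlations will be significant.
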